#### *6.4 ePROMs remote capture and review*

1. All participants will be asked to complete a RADAI-5 questionnaire via the secure online ePROMs portal once every week for the 12 week follow-up duration of the study
2. Automated weekly reminder emails will be sent via the ePROMs platform to participants to remind them to complete a RADAI-5 assessment.
3. ePROMs RADAI-5 data will be reviewed at each monthly visit, and any missing data discussed with the participant to identify any difficulties in accessing or using the ePROMs platform.

#### *6.5 Optional focus group*

Participants at their week 12 visit who express an interest in providing additional feedback on their experience of taking part in the study will be invited to take part in an optional focus group. Participants will join a meeting, either face-to-face or virtual, lasting for approximately 60 minutes. Individual (i.e. one-on-one) meetings may be arranged where participants would otherwise feel uncomfortable or inhibited in providing feedback in a group setting.

The session will be led by a study researcher, who will invite participants to reflect on their experience (positive and negative) of participating in the study, with a specific focus on:

1. Ease of use of ePROMs portal
2. Acceptability of frequency of ePROMs measurements
3. Ease of use and acceptability of Axivity AX6 and VitalPatch monitors

The meetings will not be recorded, but rather the researcher will take written notes during the meetings. Participant feedback may be transcribed verbatim, but participant feedback will be recorded in an anonymous fashion.

#### *6.6 Participant autonomy*

Participants will have full autonomy throughout this study. The participant, informed of the full information as detailed in the participant information sheet, may withdraw their consent at any time. The wishes of the participant will be respected, and would result in them exiting the study at

that point. Any data collected up to that point would be retained and analysed by the study team in line with the terms of the original participant consent form.

#### *6.7 Digital monitoring device availability*

Owing to the pilot nature of this study, limited funds are available for the purchase of monitoring devices, and supply of these devices is constrained by disruption to global supply chains. In the event that a monitoring device (i.e. Axivity AX6 monitor or VitalPatch device) or a component required for proper device use (i.e. study smartphone/charger, wrist strap, or fixation dressing) is unavailable, then provision and/or use of the affected monitoring device will be omitted from the study visit schedule. This will be recorded on the visit case report form, but will not constitute a breach of study protocol.

#### *6.8 End of study*

If the participant declines to take part in the optional focus group (section 6.5), then the week 12 visit will be their final study visit. The participant will exit the study 7 days after this visit (i.e. at the end of their final remote monitoring device measurement period).

If the participant agrees to take part in the optional focus group (section 6.5), then a further optional focus group visit will occur no later than 180 days from the date of their week 12 visit. No additional study visits are permitted between the week 12 and optional focus group visits. No blood monitoring or disease activity measurements (remote or otherwise) will be performed as part of the research study beyond 7 days after the week 12 visit. The participant will exit the study at the end of the optional focus group visit.

## **7. ADVERSE EVENTS AND SERIOUS ADVERSE EVENTS**

### *7.1 Adverse event (AE)*

Any untoward medical occurrence experienced by the participant during their participation within the study. The severity of adverse events is defined as follows:

- i. **Mild:** Symptoms noted but no disruption to normal daily activities
- ii. **Moderate:** Symptoms sufficient to disrupt normal daily activities
- iii. **Severe:** Symptoms sufficient to prevent normal daily activities

**Causality:** All adverse events should be assessed by the principal investigator or their medically qualified delegate for any causal relationship with a study procedure, namely remote ePROM or activity/physiological monitoring. Causality is defined as:

Relationship	Description
Unrelated	There is no evidence of any causal relationship
Unlikely	There is little evidence to suggest there is a causal relationship (e.g. the event did not occur within a reasonable time after administration of the trial medication). There is another reasonable explanation for the event (e.g. the participant's clinical condition, other concomitant treatment).
Possible	There is some evidence to suggest a causal relationship (e.g. because the event occurs within a reasonable time after administration of the trial medication). However, the influence of other factors may have contributed

	to the event (e.g. the participant's clinical condition, other concomitant treatments).
Probable	There is evidence to suggest a causal relationship and the influence of other factors is unlikely.
Definitely	There is clear evidence to suggest a causal relationship and other possible contributing factors can be ruled out.
Not assessable	There is insufficient or incomplete evidence to make a clinical judgement of the causal relationship.

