## 2. STUDY SUMMARY

[figure not shown]
Trial Title	Remote monitoring of disease and physical activity in rheumatoid arthritis: a pilot study
Summary of Study Design	Observational longitudinal cohort study
Summary of Participant Population	Participants with established rheumatoid arthritis with active disease commencing a new disease-modifying anti-rheumatic drug
Planned Sample Size	20 participants
Planned Number of Sites	1
Follow Up Duration	3 months
Planned Study Period	11 months
Primary Objectives	To demonstrate the feasibility of remote disease activity monitoring in participants with rheumatoid arthritis, to support a future clinical efficacy trial.
Primary endpoint:	Correlation and agreement of remote methods of disease activity measurement (patient reported outcome measures, and activity/gait/cardiorespiratory monitors) compared to face-to-face assessments of disease activity in 28 joints with C-reactive protein (DAS28-CRP) scores.
Study Intervention:	Nil (standard clinical care, observational only)

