### 6.3 Week 12 visit

1. Participants will be asked to verbally confirm their willingness to continue in the study.
2. Any change in concurrent medications will be recorded.
3. Any adverse events occurring since the last clinic visit will be recorded.
4. A researcher will then examine the participant to ascertain the 28-joint tender and swollen counts, a patient visual analogue scale, and a physician visual analogue scale, required to assess disease activity using the DAS28-CRP score (Appendix A).
5. The participant will then complete a RADAI-5 questionnaire.
6. Remote self-entered RADAI-5 data will be reviewed on the ePROMs platform (see 6.4 below)
7. The pre-filled questionnaires provided to the participant at their last visit will be collected. If the participant has not had the opportunity to complete these or has not brought them to the appointment, then they will be asked to complete the questionnaires during the study visit:
  - a. Health Assessment Questionnaire Disability Index (HAQ-DI)
  - b. FACIT-F and MFS
  - c. PHQ-2
  - d. EQ-5D-5L
8. Participants will then be reminded on how to wear and activate the remote monitoring digital tracker devices, and how to access the ePROMs portal.
9. Participants will be provided with the following devices, to wear simultaneously for 7 days following the study visit:
  - a. Axivity AX6 monitor and adhesive dressing – for application to lower back
  - b. Axivity AX6 monitor and wrist strap – for application to wrist
10. Blood tests will be taken as per below, thus avoiding additional hospital attendances for mandatory routine clinical blood monitoring during the study period. These results will be passed on to the local clinical DMARD monitoring service, and any necessary action taken by the local clinical team. In the event that a participant has blood monitoring more frequently than once every 4 weeks, then any blood tests required before the date of the next study visit will be performed by the clinical DMARD monitoring service as per usual routine practice.
  - a. Full Blood Count (FBC)
  - b. Erythrocyte sedimentation rate (ESR)
  - c. C reactive protein (CRP)

- d. Urea and electrolytes (U&Es)
- e. Liver function tests (LFTs)

11. The study smartphone and charger will be collected from the participant.

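### No adverse event enquiry is scheduled for the last AX6 wear week, and two causality examples refer to a trial medication that this observational study does not have

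*Protocol*

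**What the plan says.** **Period and exposure.** Protocol 7.1 defines an AE as "Any untoward medical occurrence experienced by the participant during their participation within the study". Each AE is to be assessed "for any causal relationship with a study procedure, namely remote ePROM or activity/physiological monitoring". The study summary (Section 2) gives the intervention as "Nil (standard clinical care, observational only".

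**Causality table (7.1).** There are six grades. The example under 'Unlikely' is that "the event did not occur within a reasonable time after administration of the trial medication". The example under 'Possible' is "because the event occurs within a reasonable time after administration of the trial medication".

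**When AEs are asked about.** Sections 6.2 and 6.3 ask at weeks 4, 8 and 12, each time looking back; the week 12 item reads "Any adverse events occurring since the last clinic visit will be recorded". The AE row in Section 15 is marked for visits 2, 3 and 4 only.

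**What happens after week 12.** Section 6.3 states: "Participants will be provided with the following devices, to wear simultaneously for 7 days following the study visit". It lists the lower-back and wrist AX6 monitors but not the VitalPatch. The AX6 devices come back by post. For a participant who declines the focus group, 6.8 states: "The participant will exit the study 7 days after this visit (i.e. at the end of their final remote monitoring device measurement period". The others stay in the study until a focus group held up to 180 days after week 12, and no study visit is allowed in between. Section 15 has no AE entry in the focus group column, and the topics listed in 6.5 are ease of use and acceptability.

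**Reporting (7.5).** All AEs go on case report forms. Every SAE goes to the Sponsor within one working day. Unexpected SAEs related to a study procedure have a further route with its own deadlines.

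**The concern.** There are two separate points, both about how device-related events are recorded.

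First, the protocol counts events in the last wear week as AEs, but nothing in the schedule asks for them. The back monitor is fixed with an adhesive dressing, so a skin reaction is the kind of event that could arise in that week. The week 12 feedback questionnaire cannot fill the gap, because it is completed before that wear period begins. If the pilot reports device-related AEs over all four wear weeks, the rate may come out too low, and this pilot is meant to inform a larger trial.

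Second, the only timing guidance in the causality table names a product the study does not give. Under the inclusion criteria (5.1) every participant is about to start, or has recently started, a DMARD. An assessor looking for the medication could therefore time the event from the DMARD rather than from device wear. These two grades lie where related and unrelated events are separated, and relatedness decides whether an unexpected SAE takes the additional route in 7.5.

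**Working it through.** The protocol states no figure for AE coverage, so there is nothing to reproduce. The check is a count of wear weeks against enquiry points, followed by a comparison of the causality texts.

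**Step 1: coverage of AX6 wear weeks.** Inputs: visit days 0, 28, 56 and 84 (Section 15), 7 days of wear after each visit (6.1 to 6.3), and AE enquiry at days 28, 56 and 84.

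| Wear week | Days | Next scheduled AE enquiry |
|---|---|---|
| 1 | 0 to 7 | day 28 |
| 2 | 28 to 35 | day 56 |
| 3 | 56 to 63 | day 84 |
| 4 | 84 to 91 | none |

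Visit windows of ±7 days do not change this. The closest two consecutive visits can fall is 14 days apart (for example days 35 and 49), which is longer than a wear week.

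Uncovered share: 1/4 = 25% of AX6 wear weeks. With 20 participants who all complete, this is 20 of 4 × 20 = 80 participant-weeks.

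**Step 2: other denominators.**
- Device-weeks per participant under 6.3, with no VitalPatch at week 12: 3 + 3 + 3 + 2 = 11, of which 2 are uncovered, so 2/11 = 18%.
- If the single device row in Section 15 is read as including the VitalPatch at visit 4: 3/12 = 25%.
- Participation time for those who decline the focus group: 7/(84 + 7) = 7/91 = 7.7%. With visit 4 at day 91 or day 77, this is 7/98 = 7.1% or 7/84 = 8.3%.
- For focus group attendees, up to 180 of 84 + 180 = 264 days (68%) follow the last enquiry. Only the first 7 of those days involve device wear.

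**Step 3: effect on a reported rate.** Assume that events are equally likely in each AX6 wear week, that every event in a solicited week is captured, and that a fraction *s* of last-week events is reported spontaneously. The documents do not give *s*. The captured share over four weeks is (3 + *s*)/4:
- *s* = 0: 75%
- *s* = 0.5: 87.5%
- *s* = 1: 100%

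If only the three solicited weeks are used in both numerator and denominator, there is no under-count from this source.

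**Step 4: causality texts side by side.** The lead-in to the table names study procedures (portal completion and monitoring). Section 2 gives no intervention. Section 7.5 also refers to study procedures. The examples in two of the six grades ('Unlikely' and 'Possible') refer to a trial medication. The other four grades mention no drug. The two examples therefore contradict the rest of the protocol.

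**The case against.** **On the last wear week.** A reader might infer that final-week harms are missed, that nobody is contacted again, or that device tolerability will look better than it is. The documents do not support any of these. Section 7.1 covers the whole of participation and 7.5 requires all AEs to be recorded, so a spontaneous report would count. Self-reporting instructions may also sit in participant materials that are not shown. Focus group attendees do have a later contact, at which good and bad experience with the monitors is invited. The protocol sets no AE-based tolerability endpoint; acceptability is assessed by questionnaire and focus group (4.2, 8.4). A rate confined to the three solicited weeks would not be biased by leaving out the fourth. Under 6.3 the last week also involves only the AX6 monitors, and 6.7 allows devices to be omitted when supply fails. What stands is narrower: no scheduled enquiry covers that week, and the focus group is optional, possibly months later, and has no AE entry.

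**On causality.** A reader might infer that two grades are defined by time since a drug, so that SAEs will be misrouted. That goes too far. The wording sits inside examples; the operative definitions are little or some evidence of a causal relationship. The lead-in names the right exposure and 7.5 repeats it. Both grades also list concomitant treatment as a competing explanation, which is the natural place for the DMARD. Every SAE reaches the Sponsor whatever its grade. What stands is that the examples contradict the lead-in and, in this population, point to an obvious wrong exposure.

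**Conclusion.** Both points hold and both are minor.

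Followed as written, the schedule leaves one of four planned AX6 wear weeks without solicited AE capture: 20 of 80 participant-weeks if all 20 complete with devices available, 2 of 11 device-weeks under 6.3, or 7 of 91 days for those who decline the focus group. Device-related events may be under-counted if that week is in the denominator. By how much depends on spontaneous reporting, which the documents do not quantify.

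Two of six causality grades carry examples that contradict the 7.1 lead-in and the absence of any study intervention. The risk is that timing is judged from the DMARD. It is limited by the correct wording in the lead-in and in 7.5.

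Neither point touches the correlation or responsiveness analyses.

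**What to change.** 1. Add a short AE form to the pre-paid envelope given at week 12, or make one telephone call at the end of that wear week, and add a matching entry in Section 15. Scheduled enquiry would then cover 4 of 4 AX6 wear weeks instead of 3 of 4. Neither option is a study visit, so the limit on visits in 6.8 is respected. The cost is one form (or call) per participant to process, at most 20.

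2. In the 'Unlikely' and 'Possible' grades of 7.1, replace the reference to giving a trial medication with: the study procedure (device wear or ePROM completion). The number of grades that mention a trial medication falls from 2 of 6 to 0 of 6. The cost is two wording changes.

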### 7.2 Serious adverse event (SAE)

Any adverse event which:

- a. Results in death
- b. Is life-threatening (i.e. an event in which the participant was at risk of death at the time of the event; it does not refer to an event which hypothetically might have caused death if it were more severe)
- c. Requires hospitalisation, or prolongation of existing hospitalisation
- d. Results in persistent or significant disability or incapacity
- e. Is a congenital anomaly or birth defect

Medical judgement should be exercised in deciding whether an adverse event/reaction should be classified as serious in other situations. Important adverse events/reactions that are not immediately life-threatening or do not result in death or hospitalisation, but may jeopardise the subject or may require intervention to prevent one of the other outcomes listed in the definition above, should also be considered serious.

### 7.3 Expected symptoms

This study will recruit participants with active rheumatoid arthritis, and as such are expected to have joint pain, joint swelling and joint stiffness. Symptoms can be expected to improve (though not necessarily completely resolve) after initiation of DMARD therapy in approximately half to three-quarters of participants, with continuation or even worsening of symptoms in the remainder of participants.

### 7.4 Protocol specifications

- i. Joint pain, joint swelling and joint stiffness will not be recorded as an adverse event
- ii. An adverse event will not be classified as a serious adverse event if it is a hospitalisation, surgical procedure or other medical intervention (whether as an inpatient, day-case, outpatient or in primary care) that was planned before the recruitment of the participant to the study

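### The unlimited exclusion of joint symptoms from adverse event recording removes device-related joint events from causality assessment and conflicts with the SAE rules for unplanned admission or incapacity

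*Protocol*

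**What the plan says.** Five parts of Protocol section 7 bear on this.

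- **7.1** defines an adverse event broadly: "Any untoward medical occurrence experienced by the participant during their participation within the study". It then requires a causality judgement: "All adverse events should be assessed by the principal investigator or their medically qualified delegate for any causal relationship with a study procedure". The procedures meant are the remote questionnaire and the activity and physiological monitoring.
- **7.2** defines a serious adverse event as "Any adverse event which" meets one of criteria (a) to (e). Criterion (c) reads "Requires hospitalisation, or prolongation of existing hospitalisation", and criterion (d) covers persistent or significant disability or incapacity.
- **7.3** gives the reason for an exemption. Participants have active disease, and about half to three-quarters should improve on their DMARD, "with continuation or even worsening of symptoms in the remainder of participants".
- **7.4(i)** states the exemption: "Joint pain, joint swelling and joint stiffness will not be recorded as an adverse event". **7.4(ii)** separately takes out of the serious class any hospitalisation, procedure or intervention "that was planned before the recruitment of the participant to the study".
- **7.5** sends every adverse event to an adverse event form. Every serious one goes to the Chief Investigator, to the sponsor within 1 working day, and to the ethics committee.

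In the 7.1 causality table, the illustrations for Unlikely and Possible refer to whether the event occurred "within a reasonable time after administration of the trial medication". Section 2 lists the study intervention as nil.

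**The concern.** Leaving expected background symptoms off the adverse event form is reasonable in a study of active rheumatoid arthritis. The difficulty is that 7.4(i) filters on the name of the symptom alone. It does not ask how serious the event was, what caused it, or whether it went beyond the expected course. The filter acts before any medically qualified person judges cause or seriousness, because both judgements apply only to events already accepted as adverse events.

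Two kinds of event are exposed. One is a joint symptom caused by a study device: sections 6.1 to 6.3 place a monitor on the wrist and another on the lower back for 7 days after each of four visits, and the wrist is one of the 28 joints in Appendix A. The other is a joint symptom bad enough to cause an unplanned admission or incapacity. At stake are the completeness of safety reporting to the sponsor and ethics committee, and a formal record of any device-related joint harm in a pilot meant to support a larger trial.

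**Working it through.** No figure in the protocol bears on this and no arithmetic applies. The check reads 7.1 to 7.5 as a chain of definitions and looks for any exception to 7.4(i).

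**Case A: a non-serious joint symptom caused by a device, such as wrist pain under the strap.**
1. It meets the broad definition in 7.1.
2. 7.4(i) says it is not to be recorded as an adverse event.
3. 7.5 records all adverse events, so an event barred from that record is in practice treated as not being one.
4. The causality judgement in 7.1 applies to adverse events, so relatedness is never assessed.
5. No other section restores it.

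Result: excluded outright by the wording. Other device effects, such as skin irritation from the adhesive, are not among the three named symptoms and remain reportable.

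**Case B: a joint symptom that leads to an unplanned admission.**
1. Under 7.4(i) the symptom is not recorded as an adverse event. Since 7.2 draws serious events from adverse events, it cannot become one. The medical-judgement paragraph in 7.2 is also worded for adverse events or reactions, so it does not override 7.4(i).
2. Under 7.2(c), hospitalisation makes an event serious. 7.4(ii) speaks of an adverse event that is itself a hospitalisation, and removes only those planned before recruitment. This implies that unplanned ones count.
3. Nothing says which rule prevails.

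Result: a contradiction. A site that reports nothing and a site that reports a serious event can each point to a section in support.

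**Case C: a joint symptom that causes incapacity without admission.**
1. 7.2(d) would make it serious and 7.4(ii) does not exempt it.
2. 7.4(i) still bars it from the adverse event record. Unlike Case B, there is no admission to report in its own right, so a site has less textual support for reporting it.

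Result: the same conflict, with a weaker route out.

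**The causality table.** The governing sentence in 7.1 names the study procedure as the reference. Two of the table's illustrations name a trial medication instead. The study has none, but section 5.1 requires every participant to be about to start, or to have recently started, a DMARD. An assessor who relied on the illustration could time an event against the wrong exposure.

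**The case against.** The strongest defence is that 7.4(i) names symptoms and not admissions. Because 7.4(ii) treats a hospitalisation as an adverse event and exempts only planned ones, a sensible site would report an unplanned admission, perhaps under a diagnosis such as disease flare. This stands in part. A reader might infer from 7.4(i) and 7.2 that serious joint events are certain never to be reported; the documents do not support that. They support a contradiction under which such an event could go unreported.

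A second defence is that the information is not lost. Joint counts, visual analogue scales and RADAI-5 are collected at all four visits, RADAI-5 is also completed weekly online, and device discomfort can be raised in the week 12 questionnaire and the optional focus group. This also stands. A reader might infer that such symptoms become invisible to the study, and they do not. But none of these channels assigns seriousness or causality, or triggers a report to the sponsor or ethics committee.

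Third, nothing in the protocol suggests that a wrist or lower-back monitor provokes joint symptoms, and the study is observational. This bears on how often the gap would matter. It does not change what the wording excludes.

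On the causality table, the medication wording appears only as an example beneath a sentence that names the correct reference. It is a minor leftover, and it does not worsen the 7.4(i) gap, because events excluded there never reach the table.

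**Conclusion.** The point holds for safety reporting. As written, 7.4(i) excludes device-related joint symptoms from adverse event recording and causality assessment. It also conflicts with 7.2(c)/(d) and 7.4(ii) for joint symptoms that lead to unplanned admission or incapacity. The passages must be reconciled.

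The size cannot be given, because the protocol states no rate for serious or device-related joint events. A reader might take the range in 7.3 as a measure: with half to three-quarters improving, 20 × (1 − 0.75) = 5 to 20 × (1 − 0.50) = 10 participants would have continuing or worse symptoms. That counts ordinary disease symptoms, which 7.3 justifies exempting and which should stay exempt. It is not a count of missed events.

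The conclusion assumes that sites apply 7.4(i) as worded and that no other study document qualifies it. No endpoint, estimate or sample size is affected.

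**What to change.** Reconcile 7.4(i) with 7.1, 7.2 and 7.4(ii) by adding to 7.4(i): *unless the event meets a criterion in 7.2 or is judged possibly, probably or definitely related to a study device or procedure*. Expected, non-serious rheumatoid arthritis symptoms remain exempt, so the purpose of 7.3 is kept.

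As a minor related correction, change the Unlikely and Possible rows of the 7.1 causality table so that timing is judged against the study procedure and not a trial medication.

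The cost is two wording changes in section 7 and a few more adverse event and serious adverse event forms. Site staff would also need to consider a possible device cause before setting a joint symptom aside. No visit, measurement or analysis changes.
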